5.0 METHODOLOGY

5.1 Patient Admission Criteria (Diagnosis / Medical Table)

Symptoms such as fever, weakness, cough, mild shortness of breath between the ages of 40-75 referring to the clinic with COVID-19 (SARS-CoV-2) test positive or atypical in CT findings. Patients with signs of pneumonia and considered COVID 19, undergoing intubation treatment in the intensive care unit, and meeting the inclusion / exclusion criteria. Patients who are not found suitable according to the intervals specified in the Inclusion / Exclusion criteria will not be included in the study.

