1.0 SUMMARY of INVESTIGATION

Study Title:	Prospective, Parallel, Multicenter Randomized Controlled Study Investigating the Effects of UVC Beam and Laser Beam Therapy According to Standard Therapy in Patients with Covid-19 Diagnosis
Study Code:	MD2020/001
Device :	Turkishbeam Model Number: 1007-001
	*: The device was produced by RD GLOBAL ARASTIRMA GELISTIRME SAĞLIK ILAÇ INSAAT YATIRIMLARI A.S.
Device Classification:	Class III
Purpose of the Study:	Clinical research study that evaluates the effect of Turkish Beam- Selective UV developed by RD GLOBAL ARASTIRMA GELISTIRME SAĞLIK ILAÇ INSAAT YATIRIMLARI A.S. use into Intravascular, Intrapulmonary, Intratracial, Intrarespiratory area. Bacteria, Fungal and Virus-based pathogens systematically to collect and evaluate specific clinical performance and safety data. In our Clinical Research, we aimed to investigate the effectiveness of the treatment group and control group mortality rates, intensive care hospitalization times, monitoring the virus load by PCR, and the treatment effectiveness of UVC

Scope of the Study:	This Clinical Research covers determining the treatment effectiveness and reliability of UVC application to patient groups, the details of which are determined in the protocol.
Application:	Intravascular, Intrapulmonary, Intratracial, Intrarespiratory UVC and Laser Therapy System
Overall Study Design:	Prospective, Parellel, Multicenter, Randomized Controlled
Number of volunteers:	50 patient- 2 groups with 25 (two hundred) patients in each group
Treatment Groups:	Test: Antiviral + Antimalarial + Antibiotic Treatment + UVC Therapy Control: Antiviral + Antimalarial + Antibiotic Treatment
Groups of Volunteer:	Those who are between the ages of 40-75 and who have applied to the clinic with symptoms such as fever, weakness, cough, and shortness of breath, or who have signs of COVID-19 (SARS- CoV-2) test positive or atypical pneumonia findings in CT findings and accepted as COVID 19 infection, and patients undergoing intubation treatment in intensive care unit
Sensitive population / Vulnerable subjects:	The study will not include under-40, pregnant women and those with suspected pregnancy, previously diagnosed with mental disorders, puerperant women and lactating women

Duration of the clinical trial: 3 months (04.2020- 07.2020)

Researched Medical Condition:

and Disease

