2.0 DESIGN of STUDY

2.1 DESIGN

Prospective, parallel, multicentre, randomized controlled study Ages between 40 and 75 years of age and positive symptoms such as fever, malaise, cough, and shortness of breath, or positive atypical pneumonia in CT findings or COVID-19 (SARS-CoV-2) test In the intensive care unit, which is accepted as COVID 19 infection and has been treated, patients will be treated with UVC radiation and laser beam treatment according to IKU principles in addition to Antimalarial therapy + Antiviral therapy + Antibiotic therapy. Standard

treatment consisting of Antimalarial therapy + Antiviral therapy + Antibiotic therapy will be applied to the control group. The dosage of the standard treatment consisting of antimalarial therapy + Antiviral therapy + Anitibiotic therapy, the number of days of treatment, and its active ingredient are indicated in the table.

Treatment in Possible / Definitive COVID 19 Cases with Pneumonia						
Oseltamivir** tb 75 mg	2x75 mg, oral	5 days 5 days				
Hydroxychloroquine, 200 mg tablet	Following 2x400 mg loading dose, 2x200 mg tablet orally	5 days				
According to the physician's d	ecision					
+\$	Day 1 500 mg, oral	5 days				
Azithromycin ***	4 days following 250 mg/day					
Severe cases that did not respo	ond to the first treatment					
Favipravir 200 mg tablet	2 x 1600 mg 2 x 600 mg	5-7 days				
Or						
Lopinavir 200 mg / ritonavir 50mg tablet	2 x 2 tablet, oral	10-14 days				

Source: COVID-19 (SARS-CoV2 INFECTION) GUIDE (Scientific Board Study) T. C. MINISTRY OF HEALTH 25 MARCH 2020

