5.2 Inclusion Criteria

- Respiratory rate ≥ 30

- Dyspnea and breathing difficulties findings

- Cases with oxygen saturation below 90% despite nasal oxygen support of 5 liters / minute and above

- Cases with partial oxygen pressure below 70 mmHg despite nasal oxygen support of 5 liters / minute and above

- PaO2 / FiO2 <300

Lactate> 4 *mmol* / *L*

Bilateral infiltrations or multi-lobar involvement on chest x-ray or tomography

- Hypotension (systolic blood pressure <90 mmHg,> 40 mmHg drop from usual SKB, mean arterial pressure <65 mmHg)

- Skin perfusion disorder

Organ dysfunction such as kidney function test, liver function test disorder, thrombocytopenia, confusion

Presence of immunosuppressive disease-

Presence of uncontrolled comorbidity with more than one feature

- Troponin height, arrhythmia
- COVID 19 Test positivity

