- The patient is given 100% oxygen for 2 minutes,
- Sterile gloves are worn,
- Steerable catheter is advanced through the airway to the orotracheal region in accordance with the aseptic technique.
- Fiberoptic UVC is advanced through the line catheter in accordance with the aseptic technique.
- When the catheter inserted through the nose or mouth reaches the pharynx, the patient is coughed and the catheter is advanced in the inspiratory phase and UVC is applied.
- The patient is monitored throughout the procedure,
- After the procedure, the patient is given 100% oxygen for 1 minute.
- The time required for the tracheal application of the energy required for the microorganism inactivation with the power value applied by the UVC source, these values are indicated in the table below according to the trachea diameter. (Table 1).

Respiratory Application Diameter Mm	Power Per Unit Area	Application time	Energy Required
Diameter (mm)	mw/cm ²	S	mj/cm ²
5	67,90	2,95	200
10	61,11	3,27	200
15	57,72	3,47	200
20	55,00	3,64	200
25	52,28	3,83	200
30	49,57	4,03	200
35	46,85	4,27	200
40	44,14	4,53	200
45	42,10	4,75	200
50	40,74	4,91	200
	(Table	1)	

Depending on the trachea diameter in the drawn CT, force should be applied for the time specified in the relevant table. The amount of energy to be transferred to the tissue is arranged according to the table with each advance of the fiberoptic catheter 1 cm.

The healthcare personnel who receive the treatment, taking into consideration the clinical condition of the patient, should not exceed the maximum application time (30 min \pm 5 min in intravascular applications, 5 min \pm 1 min in intrarespiratory applications), and this should be at most 5 days. should apply in accordance with the protocol.

CLINICAL WORK TREATMENT AND FOLLOW-UP PROGRAM								
Evaluation	Screening Visit (Day 0)	Inclusion / Randomization (Day 0)	Treatment Visit (Day 1)	Treatment Visit (Day 2)	Treatment Visit (Day 3)	Treatment Visit (Day 4)	Treatment Visit - Final (Day 5)	Label Period / Follow-up Visit (Day 7&15)
Informed Volunteer Consent Form	Х							
Demographic information	X							
Medical history / General physical examination	X	X	X	X	X	X	X	x
Current treatments (drugs)	X	X	x	x	X	X	X	
Biochemistry, Complete blood count	X	X	x	x	X	X	X	x
Radiological Imaging	X	X		X			X	X
Vital findings	X	X	X	X	X	X	X	X
Include / exclude criteria		X	X	X	Х	X	X	
Pregnancy test (serum / urine)	X	X						
randomization		X						
Dose diary			X	X	X	X	X	

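### The summary and sections 2.1, 5.1, 5.2 and 5.4.1(c) do not describe one population by ventilation status, 5.2 has no combining rule, and no analysis accounts for ventilation status

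*Combined protocol and SAP*

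**What the plan says.** Five places bear on who may enter.

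- **Summary (1.0).** After a chain of alternatives on symptoms, test and CT, it ends "accepted as COVID 19 infection, and patients undergoing intubation treatment in intensive care unit". That clause can be a further condition or a second group.
- **Section 2.1.** It places patients "In the intensive care unit, which is accepted as COVID 19 infection and has been treated". Intubation is not mentioned.
- **Section 5.1.** It opens with "Symptoms such as fever, weakness, cough, mild shortness of breath between the ages of 40-75", accepts either a positive test or CT findings, and then requires patients to be "undergoing intubation treatment in the intensive care unit, and meeting the inclusion / exclusion criteria".
- **Section 5.2.** It lists 14 items. Two are "Cases with oxygen saturation below 90% despite nasal oxygen support of 5 liters / minute and above" and "Cases with partial oxygen pressure below 70 mmHg despite nasal oxygen support of 5 liters / minute and above". None is intubation. One is a positive COVID-19 test. The only sentence linking 5.1 to the list is "Patients who are not found suitable according to the intervals specified in the Inclusion / Exclusion criteria will not be included in the study", and it gives no rule for combining the items.
- **Section 5.4.1.** Procedure b passes the catheter through the endotracheal tube. Procedure c passes it through the nose or mouth, with an airway placed for the oral route.

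The trial is described as multicentre and randomised, with no allocation method or stratification factor stated. Section 6 plans a t test or Mann-Whitney test for ICU stay and unspecified survival tests, with no covariates or strata.

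**The concern.** A site that reads only 5.1 would enrol intubated patients. A site that works from 2.1 and 5.2 could enrol any ICU patient who meets the listed items, including one still on nasal oxygen. Both could believe they were following the protocol.

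Ventilation status matters for what the trial measures. The recovery part of the primary endpoint in 5.5 requires saturation above 93% without oxygen support and a coma score of 13 or above, so a patient ventilated at entry starts further from it. ICU stay and survival are also likely to differ by ventilation status. If both kinds of patient enter, the result belongs to no defined population, and the planned tests leave a known source of variation unaddressed.

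**Working it through.** **1. Ventilation status, passage by passage**

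| Place | Ventilation status implied |
|---|---|
| Summary 1.0 | Intubated as a condition, or as a second group |
| 2.1 | ICU; intubation not stated |
| 5.1 | Intubated, in ICU, and meeting 5.2 and 5.3 |
| 5.2 | Not stated; two of 14 items are failure on nasal oxygen |
| 5.4.1 b | Endotracheal tube in place |
| 5.4.1 c | Nasal or oral route, no tube described |

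**2. Origin of the 5.2 list.** It nearly repeats the ICU admission indications reproduced in section 4.6, with test positivity added. Those indications decide who goes to intensive care. They do not decide who is intubated.

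**3. How the 5.2 items could combine**

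- *All required.* A patient would need hypotension, immunosuppressive disease, raised troponin, failure on nasal oxygen and every other item together, and be intubated under 5.1. That is close to impossible. It would also make a positive test compulsory and so remove the CT route that 5.1 allows.
- *Any one sufficient.* A patient who enters 5.1 by a positive test already meets 5.2 through the test item alone. Others need only one item, such as PaO2/FiO2 below 300. The list then adds little to 5.1.

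**4. Size if both groups enter.** The plan has no figure to reproduce: it gives no event rate, power or intubated share. Assumptions: intubated share q = 0.5, overall mortality p = 0.5, mortality gap g = 20 to 50 points. The documents give both 25 per arm (summary) and 400 in total, or 200 per arm (section 6), so both are shown.

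- Total SD of the mortality difference = sqrt(2p(1−p)/n)
- SD of the difference in intubated share = sqrt(2q(1−q)/n)
- Component due to imbalance = g × that SD
- SD after adjustment = sqrt(total² − component²)

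At n = 25:

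- Total: sqrt(2 × 0.25/25) = 14.1 points
- Component: 0.141 × 20 = 2.8, to 0.141 × 50 = 7.1 points
- After adjustment: sqrt(200 − 8) = 13.9, to sqrt(200 − 50) = 12.2 points

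At n = 200:

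- Total: sqrt(2 × 0.25/200) = 5.0 points
- Component: 0.05 × 20 = 1.0, to 0.05 × 50 = 2.5 points
- After adjustment: sqrt(25 − 1) = 4.9, to sqrt(25 − 6.25) = 4.3 points

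**5. Chance of a visible imbalance.** Exact binomial probabilities under unstratified allocation, for assumed intubated shares of 0.2 to 0.7:

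- At 25 per arm, the arms differ by at least 20 points in intubated share with probability 11% to 20%. A 20-point imbalance shifts the mortality difference by 0.2 × 20 = 4 to 0.2 × 50 = 10 points.
- At 200 per arm, a difference of at least 10 points has probability 1.5% to 5.1%.

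**The case against.** The strongest reply is that 5.1 settles the matter. It joins its requirements with a plain conjunction, so 5.2 is an added condition. Even if any one item suffices, the patient must still be intubated. This stands: a reader might infer that a single item such as immunosuppressive disease is enough for entry, and 5.1 does not allow that.

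Three other readings are tempting, and the documents do not support them.

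- *Section 5.2 defines a population on nasal oxygen.* Only two of 14 items mention it. An intubated patient can meet others, and those two may describe the state before intubation.
- *Procedure c is for a patient who coughs on request.* The text says "the patient is coughed and the catheter is advanced in the inspiratory phase" and mentions no request. Procedure b also describes coughing, with a tube in place, so cough does not separate the groups. The nasal or oral route and the airway placement are the better evidence. Even these describe technique, not eligibility. With treatment lasting up to 5 days, procedure c might be meant for patients extubated after entry, but the protocol does not say so.
- *Mixing would bias the comparison or add noise beyond ordinary sampling error.* Randomisation balances ventilation status on average, and the imbalance component is already part of the variance an unadjusted test counts.

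It is also fair that a list of ICU admission indications is not normally read as all required. But 5.2 presents the list as inclusion criteria, which normally are, and nothing in the text chooses between the two.

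**Conclusion.** The point holds as an inconsistency in the definition of the population. Section 5.1 requires intubation, 2.1 does not mention it, the summary is ambiguous, 5.2 has no combining rule and includes items that fit a patient without a tube or before intubation, and procedure c implies a patient without one. Because the all-of reading conflicts with 5.1 and its CT route, this is more than missing detail, and a multicentre trial gives room for different readings.

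The consequence is an unclear target population and, if both groups enter, some lost precision. On the stated assumptions, adjustment would reduce the SD of the mortality difference from 14.1 to between 13.9 and 12.2 points at 25 per arm, and from 5.0 to between 4.9 and 4.3 at 200 per arm. The gain is small at the lower end of the assumed gap and moderate at the upper end. The documents supply neither the intubated share nor the mortality gap, and there is no gain if only intubated patients are enrolled.

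**What to change.** - Reconcile the summary, 2.1, 5.1, 5.2 and procedure c so that they state one population. Say whether intubation at entry is required. The choice is the sponsor's.
- State how the 5.2 items combine, and whether a positive test is compulsory or CT findings suffice.
- Say which enrolled patients procedure c is meant for.
- If both intubated and non-intubated patients are eligible, record ventilation status at randomisation and stratify or adjust the survival and ICU-stay analyses by it.

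The cost is protocol wording, one baseline variable that the visit schedule does not now name, and a slightly more complex analysis. If only intubated patients are eligible, the wording alone is enough.

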5.2 Inclusion Criteria

- Respiratory rate ≥ 30

- Dyspnea and breathing difficulties findings

- Cases with oxygen saturation below 90% despite nasal oxygen support of 5 liters / minute and above

- Cases with partial oxygen pressure below 70 mmHg despite nasal oxygen support of 5 liters / minute and above

- PaO2 / FiO2 <300

Lactate> 4 *mmol* / *L*

Bilateral infiltrations or multi-lobar involvement on chest x-ray or tomography

- Hypotension (systolic blood pressure <90 mmHg,> 40 mmHg drop from usual SKB, mean arterial pressure <65 mmHg)

- Skin perfusion disorder

Organ dysfunction such as kidney function test, liver function test disorder, thrombocytopenia, confusion

Presence of immunosuppressive disease-

Presence of uncontrolled comorbidity with more than one feature

- Troponin height, arrhythmia
- COVID 19 Test positivity

5.3 Exclusion Criteria

- Under 40 years old
- *Pregnant women and those with suspected pregnancy*
- Those with a history of anaphylaxis
- Those with known DNA repair deficiencies:
- Those diagnosed with mental disorder,
- puerperant women and lactating women

5.4 Applied Treatment

5.4.1. Treatment Definition and Method

The system should be inserted into the Invamed Steerable Catheter (disposable CAMERA CATHETER) via an ultraviolet / laser light source and the fiberoptic cables connected on it. Ultraviolet / laser light from the end of the fiberoptic system destroys microorganisms (including viruses) at the end of a second-long application. The system is based on the basis of the elimination of microorganisms in these areas with a low dose of UV light / laser application from the catheter by sending it directly to the body cavities via a fresroptic catheter, intrarespiratory, intravascular (used with intracat). With the help of Invamed Steerable Catheter (Disposable Camera Catheter), UVC beam applied with a catheter inserted into the lungs and accompanying fiberoptic are interventions related to the reduction or elimination of infection. With the application of ultraviolet light / laser beam, the patient is treated with a significant reduction / destruction of the microorganism and inflammation burden in the patient's body. The proposed treatment is an antimicrobial treatment strategy, and it is recommended to combine supportive treatments with this process in terms of a holistic treatment strategy based on the clinical course of the disease. UVC and Laser application will be performed on the research arm, together with intravascular and intrarespiratory application.

Effective Dose: The blood / tissue infected with microorganism, the effective dose required to destroy the microorganism population: 2 mj / cm2 [4]

5.4.1.1. Intravascular UVC Application Process Steps:

- Hands are washed in accordance with the "Hand Hygiene and Glove Directions for Use".
- The patient is given a position in which he / she can feel comfortable according to the application area.
- A protective cover is placed under the interference area.
- Sterile Gloves are worn. IV cannula outer cover is opened.
- Fiberoptic catheter system is slowly pushed into the IV cannula.
- Approximately 5 cm cut from the tip of the catheter is adjusted to remain in the intrvascular area and UVC application is started.
- The Fiberoptic catheter is with drawn slowly after UVC administration at the specified time and strength.
- In order to apply the energy required for microorganism inactivation with the power value applied with UVC source, 200 mj / cm2 energy should be applied for 30 minutes +/- 5 minutes.

b. Open System Intratracheal UVC Application Process Steps:

- Hands are washed in accordance with "Hand Hygiene and Glove Usage Instruction",
- Endotracheal UVC application should be done with two people whenever possible. If the application is to be made by one person, the sterility of the hand, especially the fiberoptic line and the steerable (disposable camera catheter) catheter, should not be impaired.
- Disposable sterile gloves should be worn and the sterility of the fiberoptic line and the glove in the hand where the steerable catheter will be kept should be maintained.
- The ventilator hose should be hung so that it does not touch anywhere after leaving the patient.
- The sterile gloved hand should be pulled from the fiberoptic catheter package and wrapped around the hand to prevent contamination.
- Steerable Catheter should be gently advanced through the endotracheal tube
- Fiberoptic line should be advanced slowly.
- When the Steerable Catheter reaches the carina (resistance is felt and the patient usually coughs), progression should be stopped and the Steerable Catheter should be withdrawn about 1 cm.
- Afterwards, the catheter should be rotated slowly and should be gently advanced towards the pulmonary main bronchus on the side desired to be reached.
- If the patient needs a second UVC application, a separate sterile catheter should be used.
- The time required for the tracheal application of the energy required for the microorganism inactivation with the power value applied by the UVC source, these values are indicated in the table below according to the trachea diameter. (Table 1).

Respiratory Application Diameter Mm	Power Per Unit Area	Application time	Energy Required	
Diameter (mm)	mw/cm ²	S	mj/cm ²	
5	67,90	2,95	200	
10	61,11	3,27	200	
15	57,72	3,47	200	
20	55,00	3,64	200	
25	52,28	3,83	200	
30	49,57	4,03	200	
35	46,85	4,27	200	
40	44,14	4,53	200	

Depending on the trachea diameter in the drawn CT, force should be applied for the time specified in the relevant table. The amount of energy to be transferred to the tissue is arranged according to the table with each advance of the fiberoptic catheter 1 cm.

c. Orotracheal / Nasotracheal UVC Application Process Steps:

- Hands are washed in accordance with "Hand Hygiene and Glove Usage Instruction",
- The patient is given a semi-fowler position, the head is brought into a hyperextension state,
- If orotracheal UVC application will be applied, airway is placed,
- The patient is given 100% oxygen for 2 minutes,
- Sterile gloves are worn,
- Steerable catheter is advanced through the airway to the orotracheal region in accordance with the aseptic technique.
- Fiberoptic UVC is advanced through the line catheter in accordance with the aseptic technique.
- When the catheter inserted through the nose or mouth reaches the pharynx, the patient is coughed and the catheter is advanced in the inspiratory phase and UVC is applied.
- The patient is monitored throughout the procedure,
- After the procedure, the patient is given 100% oxygen for 1 minute.
- The time required for the tracheal application of the energy required for the microorganism inactivation with the power value applied by the UVC source, these values are indicated in the table below according to the trachea diameter. (Table 1).

Respiratory Application Diameter Mm	Power Per Unit Area	Application time	Energy Required
Diameter (mm)	mw/cm ²	S	mj/cm ²
5	67,90	2,95	200
10	61,11	3,27	200
15	57,72	3,47	200
20	55,00	3,64	200
25	52,28	3,83	200
30	49,57	4,03	200
35	46,85	4,27	200
40	44,14	4,53	200
45	42,10	4,75	200
50	40,74	4,91	200
	(Table	1)	

Depending on the trachea diameter in the drawn CT, force should be applied for the time specified in the relevant table. The amount of energy to be transferred to the tissue is arranged according to the table with each advance of the fiberoptic catheter 1 cm.

The healthcare personnel who receive the treatment, taking into consideration the clinical condition of the patient, should not exceed the maximum application time (30 min \pm 5 min in intravascular applications, 5 min \pm 1 min in intrarespiratory applications), and this should be at most 5 days. should apply in accordance with the protocol.

CLINICAL WORK TREATMENT AND FOLLOW-UP PROGRAM								
Evaluation	Screening Visit (Day 0)	Inclusion / Randomization (Day 0)	Treatment Visit (Day 1)	Treatment Visit (Day 2)	Treatment Visit (Day 3)	Treatment Visit (Day 4)	Treatment Visit - Final (Day 5)	Label Period / Follow-up Visit (Day 7&15)
Informed Volunteer Consent Form	Х							
Demographic information	X							
Medical history / General physical examination	X	X	X	X	X	X	X	x
Current treatments (drugs)	X	X	x	x	X	X	X	
Biochemistry, Complete blood count	X	X	x	x	X	X	X	x
Radiological Imaging	X	X		X			X	X
Vital findings	X	X	X	X	X	X	X	X
Include / exclude criteria		X	X	X	Х	X	X	
Pregnancy test (serum / urine)	X	X						
randomization		X						
Dose diary			X	X	X	X	X	
Adverse Event		X	X	X	X	X	X	X
Concomitant Therapy (UVC)			x	x	x	X	x	x
PCR sampling			X		X		X	X
Serum Antibody Level			1					X

Following the improvement of the clinical course of the patients, it is planned to take the patient's serum plasma on the 7th and 15th days, and to test and store it under suitable conditions for the antibody test.

Blood tests to be performed: Complete blood count, urea, creatinine, sodium, IL-1 β , IL-6, TNF α , TGF β potassium, chlorine, AST, ALT, total bilirubin, LDH, CPK, D-dimer, troponin, Ferritin, fibrinogen, procalcitonin, CRP values, quantitative measurement of PCR results of the source of infection

Radiological Imaging: Chest X-ray and / or Lung CT is taken. Clinical decision should be made according to history and examination findings in patients who cannot have chest X-ray and / or lung CT. (Radiological findings: Consolidation, ground glass appearance and reticulo-nodular opacity

appearance should be investigated in lung CT. Signs of pneumonia in lung graphy should be examined.)

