5.5 Primary Endpoints

• Ending the vital functions of the patient (medically accepted ex)

Or

- Gloskow Coma Level 13 and above,
- At least 3 days body temperature must have remained normal (measurement from the ear 37.5 C)
- Respiratory symptoms should be significantly improved
- The nucleic acid test must be negative in 2 consecutive tests for the respiratory pathogen (sampling interval must be more than 24 hours)
- Obvious healing of lesions with CT
- There should be no comorbidity or complications requiring hospitalization
- Without oxygen support SaO2 should be> 93%

All of its items have been realized

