5.6 Secondary Endpoints

- Hypersensitivity
- Temporary shortness of breath
- Rarely, redness of the skin is due to heat
- Edema
- Bleeding
- Embolization
- Hematoma
- Hyperpigmentation
- Ache
- paresthesia
- Superficial thrombophlebitis
- May cause urticaria or ulcers.
- Vascular rupture and perforation
- Visible scratch
- Iatrogenic injury may damage the surrounding tissues.
- Hemothorax or pneumothorax.
- Neighboring Nerve Damage Iatrogenically
- phlebitis
- Skin Burn or discoloration

If two or more adverse effects from the above adverse effects are seen, the study is terminated.

6. Statistical Evaluation:

- According to the course of the clinical trial, if we reach the research arm (100 patients), control group (100 patients), the efficacy and safety of the treatment will be examined and an interim report will be prepared. According to the results of the interim report, the clinical trial will be terminated or the clinical trial will be continued until the number of volunteers (400 in total) mentioned above is completed.
- In this interim analysis, the patients completing the study will be evaluated considering the primary and secondary endpoints stated in the protocol and the criteria are as follows:

1-Duration in intensive care

2-Survival rate

Contribution of UVC and laser beam application to the treatment of 3-COVID 19 infection and / or superinfections accompanying COVID 19 infection

The tests to be applied are as follows:

1-Difference test between two averages for intensive care stay

(Mann-Whitney U test or t test) will be used.

2-Survival analysis tests will be used for survival rate.

Accompanying 3-COVID 19 infection treatment and / or COVID 19 infection

To investigate the contribution of UVC and laser beam application to the treatment of superinfections

Chi-square test will be applied.

Descriptive statistics will also be given for demographic data.

REFERENCE STUDIES ABOUT THE APPLICATION OF UVC BEAM "in vitro, in vivo and ex vivo"

1. The Effect of UV-C Ray Reducing Pathogen Rate on Blood Platelets Apps;

Auto-immune diseases HIV 1 -2
T-lymphotropic virus types 1 and 2
Hepatitis B (HBV)
Hepatitis C (HCV)
Hepatitis A and E
Blood pathogens (Treponema pallidum)
Parvovirus B19

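### No follow-up is scheduled after Day 15, and survival and ICU duration have no horizon or censoring rule, so later deaths and ICU discharges may be missed or collected unevenly

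*Combined protocol and SAP*

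**What the plan says.** - **Schedule (section 5.4.1, treatment and follow-up table).** Treatment visits end with "Treatment Visit - Final (Day 5". One column follows, "Label Period / Follow-up Visit (Day 7&15", and it is the last. The table has no row for vital status or ICU status on any day.
- **Text below the table.** Days 7 and 15 are mentioned once, for serum sampling for antibodies, which is to be done "Following the improvement of the clinical course of the patients".
- **Population (section 1.0).** It includes "patients undergoing intubation treatment in intensive care unit".
- **Primary endpoint (section 5.5).** Either death, worded as "Ending the vital functions of the patient (medically accepted ex", or recovery on every item of a list. No time limit is given.
- **Analysis (section 6, Statistical Evaluation).** Three criteria are listed for the interim analysis. The first two are "1-Duration in intensive care" and "2-Survival rate". ICU stay is to be compared by Mann-Whitney or t test. For survival the plan says "2-Survival analysis tests will be used for survival rate". Neither criterion has a time point, a censoring date, or a rule for patients still in ICU. The analysis covers patients who complete the study, and completion is not defined.

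**The concern.** Intubated patients can plausibly remain in ICU, or die there, after Day 15. The plan asks two questions that depend on what happens then, how long patients stay in ICU and whether they survive, but schedules nothing later to answer them. A site that follows the table literally stops at Day 15. A site that reads the endpoint as open-ended continues to death or recovery. Data from the two would not be comparable.

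The consequences differ by criterion:

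- **ICU duration.** A stay unfinished at last contact has no observed length. A Mann-Whitney or t test must either treat the time so far as the full stay or drop the patient. Death before discharge is also not addressed, so an early death could enter as a short, apparently favourable stay.
- **Survival.** Survival methods can censor at last contact. If that is Day 15, the result speaks only to short-term mortality and rests on fewer deaths.
- **Primary endpoint.** A patient still ventilated at Day 15 has met neither outcome, and no later PCR or imaging is scheduled to settle it. With completion undefined, such patients might be left out of the analysis.

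**Working it through.** The plan has no figure of its own to reproduce here: it gives no event rate, ICU-stay distribution, effect size, significance level or power. The schedule gap is established by reading. The calculations below only show how large the consequence could be. Every rate, median and distribution in them is an assumption, and so is Day 28 as the comparison horizon.

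**1. Share of deaths falling after Day 15**

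With a constant hazard and 28-day mortality m, S(15) = (1 − m)^(15/28), and the late share is [m − (1 − S(15))] / m.

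| m | S(15) | Dead by Day 15 | Late share |
|---|---|---|---|
| 0.30 | 0.826 | 0.174 | 0.126 / 0.30 = 42% |
| 0.50 | 0.690 | 0.310 | 0.190 / 0.50 = 38% |
| 0.70 | 0.525 | 0.475 | 0.225 / 0.70 = 32% |

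Much of this is calendar time: as m becomes small the share tends to 13/28 = 46%. Early clustering lowers it. With a Weibull hazard of shape 0.5, the exponent 15/28 becomes (15/28)^0.5 = 0.732, and the shares fall to 23%, 20% and 16%.

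**2. Share of ICU stays running past Day 15**

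Exponential: 2^(−15/median). Lognormal with sigma 0.7: 1 − Φ(ln(15/median)/0.7).

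| Assumed median stay (days) | Exponential | Lognormal |
|---|---|---|
| 7 | 23% | 14% |
| 10 | 35% | 28% |
| 14 | 48% | 46% |
| 20 | 60% | 66% |

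**3. Effect on the ICU-stay comparison if stays are capped at last contact**

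Lognormal stays with sigma 0.7, simulated, mean difference in days:

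| Medians (control vs test) | Uncapped | Capped at Day 15 | Capped at Day 28 |
|---|---|---|---|
| 10 vs 7 | 3.8 | 2.1 | 3.2 |
| 14 vs 10 | 5.1 | 1.8 | 3.5 |
| 20 vs 14 | 7.7 | 1.5 | 3.9 |

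With 25 per arm and medians 14 vs 10, simulated Mann-Whitney power is 34% capped at Day 15 and 36% uncapped. The damage is therefore mainly to the estimate and not to the rank test.

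**4. Effect on a mortality comparison**

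Assume eventual mortality of 60% vs 40%, with 50–80% of deaths by Day 15 and 80–95% by Day 28. Of 25 × (0.6 + 0.4) = 25 expected deaths among 50 patients, 12.5 to 20 are seen by Day 15 and 20 to 23.8 by Day 28. Power uses the two-sided 5% normal approximation Φ[(d − 1.96·SE₀)/SE₁], where d is the difference in proportions dead, SE₀ its pooled and SE₁ its unpooled standard error:

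| Per arm | Deaths to Day 15 | Deaths to Day 28 |
|---|---|---|
| 25 | 13–21% | 21–27% |
| 200 | 64–91% | 91–97% |

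The two sizes correspond to the totals of 50 (section 1.0) and 400 (section 6). That conflict is a separate matter.

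**The case against.** The strongest reply is that nothing in the documents makes Day 15 the end of data collection. The table lists examinations, laboratory tests, imaging, PCR and adverse events. Since it never lists vital or ICU status, its last column cannot show when those stop being recorded. The primary endpoint is a final state without a time limit, in a trial lasting three months, so following each patient to death or recovery fits the text as well as stopping at Day 15. This stands: a reader might infer that later deaths and discharges are certainly lost, and the documents do not support that. They do not plan the later collection either, and that is the gap.

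The sentence on serum sampling could also mean that Days 7 and 15 count from clinical improvement. The table, which runs from Day 0 through Day 5 to this column, favours counting from randomisation. If the count did start at improvement, patients who never improve would have no dated follow-up.

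A reader might further infer that a treatment which only delays death past Day 15 would appear to save lives. That goes too far. The plan specifies survival methods, which use time to death and need not count a censored patient as saved. Any fixed horizon, Day 28 included, also leaves deaths beyond it unseen.

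Finally, the two criteria are two of the three listed for the interim analysis, and the declared primary endpoint is the composite in section 5.5. They should not be called the primary endpoints, although section 1.0 does name mortality and ICU time among the study aims.

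The power argument is weak at 25 per arm, where power for mortality is low at either horizon. It has force only if the larger total applies.

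**Conclusion.** The point holds as a gap in specification with a real consequence. No follow-up is scheduled after Day 15, and neither survival nor ICU duration has a horizon or a censoring rule. Followed as written, this can give truncated or uneven outcome data.

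The clearest harm is to ICU duration. Under the assumed medians of 7 to 20 days, 14–66% of stays run past Day 15, and capping there would shrink a true mean difference of 5.1 days to 1.8. For survival, censoring at Day 15 limits the conclusion to short-term mortality and loses events: 32–42% of 28-day deaths under a constant hazard, and fewer if deaths come early. These sizes rest on assumed rates, distributions and a chosen Day 28. They show that the gap could matter, not what this trial would observe.

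The documents do not support the stronger conclusion that Day 15 is the cut-off and that later outcomes are definitely missed. This is a cheap improvement that should be made.

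**What to change.** 1. State one fixed horizon, counted from randomisation, for both survival and ICU duration. Day 28 is an example; the documents give none.
2. Record vital status and the dates of ICU and hospital discharge up to that day for every randomised patient, by chart review or telephone.
3. Analyse survival to that day, censoring only at the last confirmed contact.
4. Give ICU stay a stated rule for patients still in ICU at the horizon and for death before ICU discharge. One option is ICU-free days to the horizon with death scored as zero, compared by Mann-Whitney. Another is time to ICU discharge with death as a competing event. Extending follow-up without such a rule would leave ICU duration undefined.
5. State whether Days 7 and 15 count from randomisation or from improvement.

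The cost is one record check per patient and, with Day 28, about 28 − 15 = 13 more days before the final analysis. No new visit or test is needed.
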